3.1 Trial Design

This is a multi-centre double blind, placebo-controlled randomized cross-over study comparing 6 weeks of oxytocin treatment to 6 weeks of placebo with a 6-week washout between periods. A phase II adaptive design will be used to efficiently identify promising dose schedules and obtain meaningful efficacy data. In Stage 1 of the study, we will evaluate three dosing schedules compared to placebo: daily dosing, alternate day dosing, and every 3rd day dosing. At the end of Stage 1, Bayesian analysis will be conducted to identify the most promising dose schedule, termed the “target dose”. In Stage 2, additional patients will be enrolled at the target dose schedule. In both stages the primary outcome measure is change on the NPI apathy/indifference domain score from baseline. At the end of Stage 2, data from patients receiving the target dose (from Stage 1 and Stage 2) are combined in the efficacy analysis. An optional CSF sub-study

measuring oxytocin levels during oxytocin vs. Placebo periods will confirm CSF oxytocin level rises in FTD and determine whether changes in CSF oxytocin levels correlate with behavioural measures.

The study is double blinded, participants and all study staff aside from central drug coordinator and unblinded DSMB members will be blinded to dose and arm. In Stage 2 of the study, the study staff and participants will be blinded to dose (at the suggestion of the DSMB and TSC) and arm. Randomization occurs after screening data is accessed and the participant deemed eligible but prior to baseline appointment. In some instances, this meant that participants were randomized into the trial without ever attending a baseline appointment.

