Rationale: It is recognized that naturalistic and qualitative behavioural observations are very informative in the diagnosis of FTD beyond the information provided by traditional assessments. Recent work has demonstrated the power of objective quantitative ratings of patient behaviours from in-home video assessments during mealtime by blinded trained reviewers using the Social Observation Checklist to distinguish between patients with bvFTD, AD and study partners. The Social Observation checklist includes numerous verbal and nonverbal items that we predict may be improved by oxytocin including:

- 1) spontaneous verbal behaviour,
- 2) verbal responsiveness to others' comments (i.e. reflective comments),
- 3) elaboration of verbal responses (more than minimal answers),
- 4) "others" references ("you" statements or references to family),
- 5) joint attention,
- 6) gaze/eye contact during the interaction,
- 7) facial responses appropriate to the interaction,
- 8) social tact

To obtain a naturalistic behavioural assessment independent from study partner ratings, using procedures similar to those in Mendez et al. we will obtain 1 hour videotape sessions during a meal via a non-intrusive camera placed by study personnel for the treatment and placebo arms of the study. Videotape sessions will be conducted at the study visits during a meal break with study partners in a private setting. Central raters will be trained to rate behaviours using the Social Observation Checklist blinded to treatment and visit status.

Other measures:

- Change in Serum Estradiol and Testosterone Levels

Rationale: Estrogen is known to modulate oxytocin binding in regions of the limbic system. Interactions between testosterone and oxytocin have also been suggested in human studies. We will obtain estradiol and free testosterone and total testosterone measurements at each baseline and the end of treatment periods to examine potential interactions of these hormone levels with the effects of oxytocin administration.

- Genetic Testing for Oxytocin Polymorphisms

Rationale: Polymorphisms in the oxytocin receptor may account for some of the heterogeneity of response to intranasal oxytocin observed across studies. We will examine genetic polymorphisms related to oxytocin function including the most common rs53576 SNP, for which GG homozygosity has been linked to increased empathic responses, and greater response to intranasal oxytocin compared to AA allele carriers.

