6.2 Analysis Methods

The primary analysis of the change from baseline NPI apathy domain is based on a linear model with covariates for sex and order of treatment in the crossover including data from both Stage 1 and Stage 2 for the target selected treatment arm (ETD) will be used to demonstrate superiority using a nominal 2.5% one-sided test using the PPP. Estimated mean effect of the treatment compared to placebo and 95% confidence intervals will be reported. Analysis will compare relative period effects for PBO and OXY periods via change in scores from Baseline to End of Treatment visit.

Supportive primary analysis will be conducted on the MITT population. Given the crossover design, the ITT analysis excludes those that did not take any study medications in their second treatment period.

Sensitivity analysis combining all dose groups for OXY vs. PBO will be conducted for all primary, secondary, and exploratory outcome measures.

Covariates:

Order of treatment (End of treatment 2: Oxytocin versus End of Treatment 2: Placebo)

Sex (male vs female)

Subgroup analyses:

By sex

By severity

Age (median split : young <67 years; older 67+ years)

Oxytocin Genetic polymorphism (GG vs AG vs AA)

FTD subtype (bvFTD vs PNFA vs SD)

ALL other outcomes as listed above, will be analysed using the same methods as for the primary outcome using 5% 2-sided test. Subject is modeled as a random effect, the others are all fixed effects.

To explore whether hormonal levels or imaging atrophy patterns predict behavioural response to OXY, we will conduct a linear regression with NPI apathy domain change scores for OXY-PBO as the dependent measure and predictors of regional MRI atrophy ratings (scores from the Harper et al. visual rating scale for each of the following regions: orbitofrontal, rostral anterior cingulate, fronto-insula, medial temporal, and posterior), baseline serum estrogen level (continuous), baseline serum testosterone level (continuous), sex, and treatment order.

The following endpoints are included in the prospective analysis plan:

Table 6.1A. Endpoints for Analysis

#	Endpoint	Role	Endpoint Type	Pop	Model

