8	NPI – Apathy Doman Change Score	Primary Efficacy Endpoint SUBGROUP	Continuous Outcome. Higher scores represent worse apathy values.	PPP Most promising dose group (Q3D) from stage 1 and stage 2	$Y_{\text{period}} = \text{Intercept} + \text{period2} + \text{subject} + \text{female} + \text{OXY}$ OXYTOCIN GENE rs53576 AA vs GG vs AG
9	NPI – Apathy Doman Change Score	Primary Efficacy Endpoint SUBGROUP	Continuous Outcome. Higher scores represent worse apathy values.	PPP Most promising dose group (Q3D) from stage 1 and stage 2	$Y_{\text{period}} = \text{Intercept} + \text{period2} + \text{subject} + \text{female} + \text{OXY}$ By FTD clinical subtype: bvFTD vs. svPPA vs. nfPPA
[P u bl is h D at e] 10	EFER	Secondary Efficacy Endpoint	Categorical	PPP Most promising dose group (Q3D) from stage 1 and stage 2	$Y_{\text{period}} = \text{Intercept} + \text{period2} + \text{subject} + \text{female} + \text{OXY}$
11	EFER	Secondary Efficacy Endpoint Sensitivity	Categorical	PPP All doses combined	$Y_{\text{period}} = \text{Intercept} + \text{period2} + \text{subject} + \text{female} + \text{OXY}$
12	EFER	Secondary Efficacy Endpoint Sensitivity	Categorical	MITT Most promising dose group (Q3D) from stage 1 and stage 2	$Y_{\text{period}} = \text{Intercept} + \text{period2} + \text{subject} + \text{female} + \text{OXY}$

13	IRI – Empathic Concern	Secondary Efficacy Endpoint	Continuous outcome. Higher scores represent better values.	PPP Most promising dose group (Q3D) from stage 1 and stage 2	$Y_{\text{period}} = \text{Intercept} + \text{period2} + \text{subject} + \text{female} + \text{OXY}$
14	IRI – Empathic Concern	Secondary Efficacy Endpoint Sensitivity	Continuous outcome. Higher scores represent better values.	PPP – all doses	$Y_{\text{period}} = \text{Intercept} + \text{period2} + \text{subject} + \text{female} + \text{OXY}$
15	IRI – Empathic Concern	Secondary Efficacy Endpoint Sensitivity	Continuous outcome. Higher scores represent better values.	MITT Most promising dose group (Q3D) from stage 1 and stage 2	$Y_{\text{period}} = \text{Intercept} + \text{period2} + \text{subject} + \text{female} + \text{OXY}$
16	IRI - Total Score	Secondary Efficacy Endpoint	Continuous outcome. Higher scores represent better values.	PPP Most promising dose group (Q3D) from stage 1 and stage 2	$Y_{\text{period}} = \text{Intercept} + \text{period2} + \text{subject} + \text{female} + \text{OXY}$

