	Total Score		from 0,1,2,3,4). Higher scores represent worse outcome		
44	NPI – Apathy Doman Change Score	Exploratory biomarker predictors of response	Continuous Outcome. Higher scores represent worse apathy values.	PPP all dose groups combined	$Y_{\text{period}} = \text{Intercept} + \text{period2} + \text{subject} + \text{female} + \text{OXY}$ Linear regression model: Dependent variable: change in NPI Apathy domain scores during OXY – PLC period. Predictor variables: OXT receptor genotype, serum estrogen (baseline), serum testosterone (baseline), change in CSF_oxy, MRI regional atrophy ratings, age, sex, treatment order. -OXYTOCIN GENE rs2254298 AA vs GG vs AG -MRI atrophy ratings (frontal right, frontal left, temporal right, temporal left, etc.)
45	ACE-III	Exploratory Analysis	Continuous Outcome. Higher scores represent better cognition	PPP Most promising dose group (Q3D) from stage 1 and stage 2	$Y_{\text{period}} = \text{Intercept} + \text{period2} + \text{subject} + \text{female} + \text{OXY}$
46	ACE-III	Exploratory Analysis Supportive	Continuous Outcome. Higher scores represent better cognition	MITT Most promising dose group (Q3D) from stage 1 and stage 2	$Y_{\text{period}} = \text{Intercept} + \text{period2} + \text{subject} + \text{female} + \text{OXY}$
47	ACE-III	Exploratory Analysis	Continuous Outcome. Higher scores represent better cognition	PPP – all dose groups combined	$Y_{\text{period}} = \text{Intercept} + \text{period2} + \text{subject} + \text{female} + \text{OXY}$
48	QTcF interval as measured by ECG	Safety Outcome	Continuous < change	mitT	ECG = $Y_{\text{period}} = \text{Intercept} + \text{period2} + \text{subject} + \text{female} + \text{OXY}$ Y_{period} is QTcF interval as measured by EVG, change from baseline in each period.

49	QTcF interval as measured by ECG	Safety Outcome sensitivity	Continuous < change	miITT removing participants outside of >25 minutes post dose	$Y_{\text{period}} = \text{Intercept} + \text{period2} + \text{subject} + \text{female} + \text{OXY}$ Y_{period} is QTcF interval as measured by ECG, change from baseline in each period.
50	serum sodium level	Safety Outcome	Continuous < change	miITT	$Y_{\text{period}} = \text{Intercept} + \text{period2} + \text{subject} + \text{female} + \text{OXY}$ Y_{period} is serum sodium level, change from baseline in each period.

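### The exploratory predictor regression is specified in two different ways, and row 44's CSF term limits it to sub-study participants despite its stated per-protocol population

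*SAP*

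**What the plan says.** The text of section 6.2 states that "we will conduct a linear regression with NPI apathy domain change scores for OXY-PBO as the dependent measure". Its atrophy predictors are the ratings for "orbitofrontal, rostral anterior cingulate, fronto-insula, medial temporal, and posterior", and the rest are "baseline serum estrogen level (continuous), baseline serum testosterone level (continuous), sex, and treatment order". It has no genotype, CSF or age term.

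Table 6.1A row 44, in the same section, gives the same dependent variable. Its predictors are receptor genotype, baseline estrogen and testosterone, and then "change in CSF_oxy, MRI regional atrophy ratings, age, sex, treatment order". The ratings are described there as left and right frontal and temporal, with the list left open. The SNP is given as "OXYTOCIN GENE rs2254298 AA vs GG vs AG". The stated population is the per-protocol set with all doses pooled. The cell also carries the formula used throughout the table, with terms for subject, second period, female and oxytocin.

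On CSF, section 3.1 describes "An optional CSF sub-study", and section 6.1 says levels are measured in those who consent, in both phases. On genotype, section 6.1 speaks of polymorphisms "including the most common rs53576 SNP" and gives a hypothesis for that SNP. Subgroup row 8 uses "OXYTOCIN GENE rs53576 AA vs GG vs AG".

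**The concern.** An analyst holding both descriptions cannot tell which model was planned. The two lists differ in three predictors and in how atrophy is measured, and row 44's atrophy list is not closed. That leaves room to choose among models after seeing results.

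The CSF term has a further effect. An ordinary linear regression drops any participant who lacks a value on any predictor. Under row 44, the hormone, imaging and genotype coefficients would therefore be estimated only in people who accepted CSF sampling, while the table labels the result as coming from the full per-protocol set. If the sub-study is small, the model also has too many terms for its data.

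**Working it through.** The SAP gives no sample size, power or degrees of freedom for this regression, so there is no figure to reproduce. The check counts parameters and then varies the number of complete cases.

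**Parameters, intercept included**

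- Section 6.2 text: 1 + 5 regions + 2 hormones + sex + order = 10. With left and right entered separately: 1 + 10 + 2 + 1 + 1 = 15.
- Row 44: 1 + genotype 2 (three levels) + estrogen 1 + testosterone 1 + CSF change 1 + ratings k + age 1 + sex 1 + order 1 = 9 + k. This is 13 with the four ratings named in the row (k = 4), 14 with five regions, and 19 with five regions by side.

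**Who can be in the row 44 fit.** CSF change is taken as the difference between the two treatment periods, so both samples are needed. Section 6.3 assumes data missing at random and uses the observed records. It states no imputation of predictors, so it does not bring back people without CSF.

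**Residual degrees of freedom = n − parameters.** Section 4 plans 60 participants in Stage 1 and 40 in Stage 2, so 60 + 40 = 100 is a ceiling. The smaller values of n are assumptions, because CSF uptake is not given.

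| Complete cases | 13 parameters | 14 parameters | 19 parameters |
|---|---|---|---|
| 100 | 87 | 86 | 81 |
| 60 | 47 | 46 | 41 |
| 40 | 27 | 26 | 21 |
| 25 | 12 | 11 | 6 |
| 20 | 7 | 6 | 1 |
| 15 | 2 | 1 | not estimable |

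**What this means with 14 parameters**

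- Expected R-squared when no predictor matters is 13/(n − 1): 13/19 = 0.68 at n = 20, 13/39 = 0.33 at n = 40, and 13/99 = 0.13 at n = 100.
- The smallest partial correlation detectable with 80% power at two-sided 0.05 (noncentral t) is 0.81 at n = 20, 0.50 at n = 40 and 0.29 at n = 100.

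**After moving CSF change out.** Row 44 with five regions falls to 14 − 1 = 13 parameters, leaving at most 100 − 13 = 87 degrees of freedom. The section 6.2 list leaves at most 100 − 10 = 90. A sub-study model with CSF change, sex and order has 4 parameters, leaving 20 − 4 = 16 at n = 20 and 40 − 4 = 36 at n = 40.

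**The formula in row 44.** The dependent variable is one difference per participant. The oxytocin indicator then does not vary between records, a subject effect cannot be separated from residual error, and a period indicator has no meaning because treatment order takes its place. The formula and the regression cannot both be the model.

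**The case against.** Several stronger readings are tempting, and the SAP does not support them.

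- **Hormone and imaging questions are answered only in CSF consenters.** A reader of row 44 alone might infer this. The section 6.2 text specifies a regression without CSF, and if that is followed the restriction does not arise. The defect is that the two descriptions disagree.
- **The model is overfitted.** This depends on uptake. Residual degrees of freedom are few at about 25 complete cases or fewer, but not at 40 or more with five regions.
- **The hypothesised SNP has been dropped.** Row 8 analyses rs53576 in the target-dose per-protocol set, without a CSF term. The wording in section 6.1 allows further SNPs, and the section 6.2 regression has no genotype term to conflict with. What stands is that rs2254298 appears only in row 44, without a reason. The choice of SNP does not shrink the sample; only the CSF term does.
- **Removing CSF change restores all 100 participants.** The per-protocol definition requires every visit and at least 70% compliance in both periods. Section 3.4 reports enrolment difficulty. Section 5.1 admits participants on CT or on a known mutation, so MRI ratings may be missing for some.

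It is also fair to say that the formula in row 44 is probably a template repeated down the table, and that the row is labelled exploratory. Both points limit the importance of the finding. Neither tells the analyst which model to fit.

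**Conclusion.** The concern holds in a limited form. Section 6.2 and row 44 give different predictor lists and atrophy variables for one regression. Row 44 as written can be fitted only in participants with CSF data in both periods, contrary to its stated population. These two conclusions come from the text and do not depend on uptake, apart from assuming an ordinary complete-case regression with no imputation of predictors.

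The size of the loss is conditional: with five regions, 6 residual degrees of freedom at 20 complete cases and 26 at 40. The misplaced formula and the unexplained SNP are smaller drafting faults in the same cell. This is a minor point, because no primary, secondary or safety conclusion rests on row 44.

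**What to change.** - Use one closed predictor list in the section 6.2 text and in row 44, with the five atrophy regions already named in 6.2. Say whether left and right are combined, and whether age and genotype are included.
- Remove CSF change from row 44 and fit it in a separate sub-study regression with CSF change, sex and order. This agrees with section 3.1, which makes the link between CSF change and behaviour an aim of the sub-study.
- Delete the period-level formula from row 44.
- Reconcile which SNP or SNPs row 44 uses with section 6.1 and row 8, and give a reason for rs2254298 if it stays.

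The cost is SAP wording and one extra exploratory row. The main predictor model would no longer adjust for CSF change. The changes should be settled before these exploratory data are examined, so that the model is not chosen on its results.

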6.3 Missing Data

NPI apathy is assessed at screening and then at each baseline visit *before study drug administration and at end of treatment visits *after study drug administration.

Schedule: Baseline 1 Visit: 6 weeks on treatment then End of Treatment 1 visit, then 6 weeks washout to Baseline 2 then 6 weeks on treatment and then End of treatment 2 visit.

Missing data will be approached with the assumption that it is Missing at Random. The statistical models incorporate each observed observation and sensors unobserved observations.

6.4 Harms

Investigators will assess the occurrence of adverse events and serious adverse events at all patient evaluation time points during the study. All adverse events and serious adverse events, whether volunteered by the patient, discovered by study personnel during questioning, or detected through physical examination, laboratory test, or other means, will be recorded in the patient's medical record and on the appropriate adverse event or serious adverse event eCRF. Each recorded adverse event or serious adverse event will include a description of its duration (i.e., start and end dates), severity, seriousness according to regulatory criteria, if applicable, and suspected relationship to the investigational product, as well as any actions taken. All AEs will be recoded into terms using MEDdra. Type and overall frequency of adverse events under each intervention will be described and analyzed using McNemar's test. Concordant and discordant pairs of adverse events and where appropriate, estimates of effect and precision will help to inform the relative safety of the intervention.

Adverse event	No of adverse events
Zero adverse events under either OXY or placebo	
Adverse event observed under placebo but not under OXY	
Adverse event observed under OXY but not under placebo	
Adverse event observed under both OXY and placebo	

November 23, 2023

Signature: PI [name]

Date

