4.1 Confidence Intervals and P-values

Stage 1 and Stage 2 for the target selected treatment arm will be used to test superiority using a nominal 2.5% one-sided test for the primary outcome of change in NPI.

All secondary, safety and exploratory outcomes will be reported as two-sided tests with statistical significance set at a two-sided 0.05 level.

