1	NPI – Apathy Domain Change Score	Primary Efficacy Endpoint	Continuous Outcome. Higher scores represent worse apathy values.	PPP Most promising dose group (Q3D) from stage 1 and stage 2	$Y_{\text{period}} = \text{Intercept} + \text{subject} + \text{period2} + \text{female} + \text{OXY}$ The intercept covers the reference group of placebo, period #1, and male. The “OXY” is an indicator of treatment – OXY. The Period2 is an indicator of it being the second period. The ‘female’ is an indicator of female patient. Y_{period} represents the NPIA domain score at End of Treatment for that period – score at Baseline for that period
2	NPI – Apathy Domain Change Score	Primary Efficacy Endpoint Supportive Analysis	Continuous Outcome. Higher scores represent worse apathy values.	MITT Most promising dose group (Q3D) from stage 1 and stage 2	$Y_{\text{period}} = \text{Intercept} + \text{period2} + \text{subject} + \text{female} + \text{OXY}$
3	NPI – Apathy Domain Change Score	Primary Endpoint Sensitivity Analysis	Continuous Outcome. Higher scores represent worse apathy values.	PPP – all dose groups combined	$Y_{\text{period}} = \text{Intercept} + \text{period2} + \text{subject} + \text{female} + \text{OXY}$
4	NPI – Apathy Domain Change Score	Primary Efficacy Endpoint Sensitivity Analysis	Continuous Outcome. Higher scores represent worse apathy values.	PPP exclude all new behaviour meds Most promising dose group (Q3D) from stage 1 and stage 2	$Y_{\text{period}} = \text{Intercept} + \text{period2} + \text{subject} + \text{female} + \text{OXY}$
5	NPI – Apathy	Efficacy Endpoint	Continuous Outcome.	PPP	$Y_{\text{period}} = \text{Intercept} + \text{period2} + \text{subject} + \text{female} + \text{OXY}$

	Doman Change Score	SUBGROUP	Higher scores represent worse apathy values.	Most promising dose group (Q3D) from stage 1 and stage 2	BY SEX (M/F)
6	NPI – Apathy Doman Change Score	Efficacy Endpoint SUBGROUP	Continuous Outcome. Higher scores represent worse apathy values.	PPP Most promising dose group (Q3D) from stage 1 and stage 2	$Y_{\text{period}} = \text{Intercept} + \text{period2} + \text{subject} + \text{female} + \text{OXY}$ BY SEVERITY (CDR 0-1 vs 2)
7	NPI – Apathy Doman Change Score	Efficacy Endpoint SUBGROUP	Continuous Outcome. Higher scores represent worse apathy values.	PPP Most promising dose group (Q3D) from stage 1 and stage 2	$Y_{\text{period}} = \text{Intercept} + \text{period2} + \text{subject} + \text{female} + \text{OXY}$ BY AGE (0-65 vs >65)

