17	IRI - Total Score	Secondary Efficacy Endpoint	Continuous outcome. Higher scores represent better values.	PPP – all dose groups	$Y_{\text{period}} = \text{Intercept} + \text{period2} + \text{subject} + \text{female} + \text{OXY}$
18	IRI - Total Score	Secondary Efficacy Endpoint sensitivity	Continuous outcome. Higher scores represent better values.	MITT Most promising dose group (Q3D) from stage 1 and stage 2	$Y_{\text{period}} = \text{Intercept} + \text{period2} + \text{subject} + \text{female} + \text{OXY}$
19	RSMS Total	Secondary Efficacy Endpoint	Continuous outcome. Higher scores represent better values.	PPP Most promising dose group (Q3D) from stage 1 and stage 2	$Y_{\text{period}} = \text{Intercept} + \text{period2} + \text{subject} + \text{female} + \text{OXY}$
20	RSMS Total	Secondary Efficacy Endpoint	Continuous outcome. Higher scores represent better values.	PPP – all dose groups	$Y_{\text{period}} = \text{Intercept} + \text{period2} + \text{subject} + \text{female} + \text{OXY}$
21	RSMS Total	Secondary Efficacy Endpoint Sensitivity	Continuous outcome. Higher scores	MITT Most promising dose group (Q3D) from stage 1 and stage 2	$Y_{\text{period}} = \text{Intercept} + \text{period2} + \text{subject} + \text{female} + \text{OXY}$

			represent better values.		
22	RSMS Total	Secondary Efficacy Endpoint sensitivity	Continuous outcome. Higher scores represent better values.	PPP – excluding those with obvious validity issues	$Y_{\text{period}} = \text{Intercept} + \text{period2} + \text{subject} + \text{female} + \text{OXY}$
23	CGIC – Apathy score	Secondary Efficacy Endpoint	Ordinal Outcome (1,2,3,4,5,6,7). 1 (marked improvement) to 7 (marked worsening)	PPP Most promising dose group (Q3D) from stage 1 and stage 2	General Estimating Equation
24	CGIC – Apathy score	Secondary Efficacy Endpoint sensitivity	Ordinal Outcome (1,2,3,4,5,6,7). 1 (marked improvement) to 7 (marked worsening)	PPP – all dose groups	$Y_{\text{period}} = \text{Intercept} + \text{period2} + \text{subject} + \text{female} + \text{OXY}$
25	CGIC – Apathy score	Secondary Efficacy Endpoint sensitivity	Ordinal Outcome (1,2,3,4,5,6,7). 1 (marked improvement) to 7 (marked worsening)	MITT Most promising dose group (Q3D) from stage 1 and stage 2	$Y_{\text{period}} = \text{Intercept} + \text{period2} + \text{subject} + \text{female} + \text{OXY}$

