51	heart rate	Safety Outcome	Continuous < change	miITT	$Y_{\text{period}} = \text{Intercept} + \text{period2} + \text{subject} + \text{female} + \text{OXY}$ For following periods: Y_{period} is HR, change from baseline in each period.
52	Systolic blood pressure	Safety Outcome	Continuous < change	miITT	$Y_{\text{period}} = \text{Intercept} + \text{period2} + \text{subject} + \text{female} + \text{OXY}$ Y_{period} is SBP, change from baseline in each period.
53	Diastolic blood pressure	Safety Outcome	Continuous < change	miITT	$Y_{\text{period}} = \text{Intercept} + \text{period2} + \text{subject} + \text{female} + \text{OXY}$ Y_{period} is DBP, change from baseline in each period.
54	Change in CSF Oxytocin Levels	Exploratory	Continuous	PPP	$Y_{\text{period}} = \text{Intercept} + \text{period2} + \text{subject} + \text{female} + \text{OXY}$ Y_{period} is HR, change from baseline in each period.
55	Adverse Events	Safety Outcome		ITT all dose groups	Counts per OXY and PLC periods, McNemar's test (see below)

56	Serious Adverse Events	Safety Outcome		ITT all dose groups	Counts per OXY and PLC periods McNemar's test (see below)
57	Withdrawal Rate	Safety		ITT all dose groups	Withdrawal counts= ED, EOD, ETD, P
58	Compliance	Safety		ITT all dose groups	Percentage of treatments taken for each dose schedule and period, t-tests

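### Adverse events are compared by McNemar's test with no period adjustment, although every model written out in Table 6.1A carries a period term; a period-adjusted paired analysis for row 55 would be a cheap improvement

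*SAP*

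**What the plan says.** Section 6.4 (Harms) states: "Type and overall frequency of adverse events under each intervention will be described and analyzed using McNemar's test". Table 6.1A repeats this for adverse events in row 55 ("Counts per OXY and PLC periods, McNemar's test (see below") and in the same terms for serious adverse events in row 56, both in the ITT population with all dose groups.

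The layout in 6.4 has four cells defined by treatment, for example "Adverse event observed under OXY but not under placebo". Nothing in it identifies the period or the sequence. Section 4.1 makes the comparison a formal one: "All secondary, safety and exploratory outcomes will be reported as two-sided tests with statistical significance set at a two-sided 0.05 level".

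The oxytocin-placebo models in the same table handle period explicitly. Row 1 explains that "The Period2 is an indicator of it being the second period", and the same term appears in every model written out, including QTcF, sodium, heart rate and blood pressure (rows 48-53). Two other rows show no period term: row 23 (CGIC apathy) gives only "General Estimating Equation", and row 58 (compliance) gives "Percentage of treatments taken for each dose schedule and period, t-tests".

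Section 6.2 also has a general rule: "ALL other outcomes as listed above, will be analysed using the same methods as for the primary outcome using 5% 2-sided test".

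**The concern.** McNemar's test pools the discordant participants of both sequences. It assumes that, with no drug effect, a participant with an event in one period only is equally likely to have had it on oxytocin or on placebo. A period effect breaks this assumption. If events are reported more often in period 1, the oxytocin-first sequence leans towards oxytocin-only events and the placebo-first sequence towards placebo-only events. The two cancel only if the sequences are equal in number, and even then the test's variance is wrong.

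At stake is the reading of the overall adverse-event comparison. A period effect could look like a drug effect, or a real excess on oxytocin could be understated. The second error is the worse one in a harms analysis.

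**Working it through.** **Inputs from the SAP.** Two-sided level 0.05 (section 4.1). Planned N = 3 x 20 + 40 = 100 (section 4). Randomisation is blocked and stratified (section 3.2), but the ratio of the two orders is not stated. Withdrawn participants are not replaced (section 5.2).

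**Assumed, because the SAP gives no figure.** Event rates, the period effect, and the sequence split among participants with both periods (50:50, with a range from 40:60 to 60:40, oxytocin-first given first).

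**Notation.** n1 = oxytocin-first and n2 = placebo-first participants with both periods. With no drug effect, a = P(event in period 1 only) and b = P(event in period 2 only).

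**1. The stated level.** With a = b, McNemar's large-sample size is 0.0500 (simulated 0.050; the exact version gives 0.036 because of discreteness). The SAP's 5% is reproduced when there is no period effect.

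**2. Unequal sequences.** E(oxytocin-only minus placebo-only) = (n1 - n2)(a - b). Take event rates of 50% in period 1 and 30% in period 2, independent within participant. Then a = 0.5 x 0.7 = 0.35 and b = 0.3 x 0.5 = 0.15.
- 60:40: oxytocin-only 60 x 0.35 + 40 x 0.15 = 27; placebo-only 60 x 0.15 + 40 x 0.35 = 23. The difference is 4 = 20 x 0.20, a false odds ratio of 1.17, with size 0.077.
- 55:45: 26 against 24, a false odds ratio of 1.08, with size 0.050.

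**3. Equal sequences.** The expected difference is zero. McNemar uses variance (n1 + n2)(a + b), but the true variance is (n1 + n2)[(a + b) - (a - b)^2]. Here the ratio is (0.50 - 0.04)/0.50 = 0.92 and the size is 0.041. This depends on sequence sizes held near-fixed by blocking, as in this trial. Under simple randomisation the unconditional size stays near nominal (0.049 simulated).

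**4. The estimate, true odds ratio 2.5, same rates on placebo.**
- Oxytocin-first: period 1 odds are 1 x 2.5, so the rate is 0.714. Oxytocin-only = 0.714 x 0.7 = 0.500; placebo-only = 0.286 x 0.3 = 0.086. Ratio 5.83.
- Placebo-first: period 2 odds are 0.429 x 2.5 = 1.071, so the rate is 0.517. Oxytocin-only = 0.517 x 0.5 = 0.259; placebo-only = 0.5 x 0.483 = 0.241. Ratio 1.07.
- Pooled at 50:50: (0.500 + 0.259)/(0.086 + 0.241) = 2.32. At 45:55 it is 2.14.
- Period-adjusted: the square root of 5.83 x 1.07 = 2.50.

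**5. With variation between participants.** Simulations with N = 100 having both periods, placebo log-odds -1.5 and subject SD 1. Adjusted means the Mainland-Gart test.

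| Split | Period odds ratio | True odds ratio | McNemar | Adjusted |
|---|---|---|---|---|
| near-equal | 2 | 1 | size 4.3-5.0% | size about 5% |
| 50:50 | 2 | 2.5 | estimate about 2.4, power 78.2% | power 77.4% |
| 50:50 | 3-4 | 2.5 | estimate 2.25-2.14 | estimate about 2.5 |
| 45:55 | 2-3 | 2.5 | estimate 2.24-2.03, power 71-64% | power 76-72% |
| 60:40 | 3-4 | 1 | false odds ratio 1.22-1.28, size 8-10% | size 5.0-5.3% |
| 40:60 | 3-4 | 2.5 | estimate 1.85-1.69, power 52-40% | power 71-66% |

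**6. How much imbalance is needed.** If the orders start at 50:50, a 55:45 split among completers needs about 9 of 50 lost from one sequence and none from the other (50/91 = 55%). A 60:40 split needs about 17 of 50 (50/83 = 60%).

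**7. Sparse events.** With 5-8 discordant participants expected (assumed for serious events, no drug or period effect), the Mainland-Gart chi-square is undefined in about 6-21% of runs. An exact version rejects in only 0.4-1.5% under the null, against 1.2-1.9% for exact McNemar.

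**The case against.** McNemar's test is a standard paired test for a binary outcome, and the SAP states no period effect on adverse events and no imbalance. Blocking keeps the sequences near-equal at entry, and 60:40 would need heavily one-sided withdrawal that would also leave about 83 pairs rather than 100. At milder inputs little changes. At 50:50 with a period odds ratio of 2, the adjusted test has slightly less power than McNemar, so equal sequences affect the estimate and the null calibration but do not cost detection. Section 6.4 does not commit to the discordant-pair odds ratio; it offers effect estimates only where appropriate. The trial is a phase 2 proof of concept, and this SAP ties no decision rule to the adverse-event test. All of this stands, and it limits the size of the point.

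Three stronger readings are tempting and not supported:
- A reader might infer that the adverse-event tests alone omit period. Rows 23 and 58 show no period term either.
- A reader might infer that 6.4 contradicts the general rule in 6.2. That rule extends a model for change scores, while 6.4 and rows 55-56 name a specific method for event occurrence, and the specific statement governs.
- A reader might infer a false-positive rate of 8-10%. That needs a strong period effect and a 60:40 split together, and the SAP gives neither.

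What the objection does not remove is the mechanism. The SAP adjusts continuous safety measures for period and gives no reason for treating adverse events otherwise.

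**Conclusion.** The point holds as a cheap improvement of minor severity. Row 55 uses a paired test that is correct only if event reporting does not differ by period, or, for freedom from bias under the null, if the sequences are equal. The adjusted alternative holds its level in the settings tried.

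The size depends entirely on assumed inputs (N = 100, placebo log-odds -1.5, subject SD 1). It is small for near-equal sequences with a period odds ratio of 2. It is noticeable at 45:55 with period odds ratios of 2-3, where an odds ratio of 2.5 is seen as 2.24-2.03 with 5-8 points less power than the adjusted test. It is large only at 60:40 or 40:60 with period odds ratios of 3-4. The direction is not fixed: a first-period excess with more oxytocin-first completers inflates the apparent harm, and with more placebo-first completers it hides one.

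**What to change.** - **Table in 6.4:** keep the four cells and show them separately for the oxytocin-first and placebo-first sequences.
- **Row 55:** replace McNemar's test with a period-adjusted paired analysis, either Mainland-Gart on discordant participants (sequence by period of the event) or conditional logistic regression with OXY and period2. Report the odds ratio with its 95% CI.
- **Row 56:** show serious adverse events by sequence and keep exact McNemar or description, because the adjusted test is unreliable or undefined with few discordant participants.
- **Section 6.2:** add a clause excepting adverse events from the general rule, so that it and 6.4 read consistently.

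The cost is a few sentences of SAP text and a few lines of code, with no new data. The statistical price is up to about 2 points of power if there is no period effect, and about 1-3 points at 50:50 when there is one. The adjusted test also gives up the extra rejections that unadjusted McNemar gains when sequence imbalance happens to favour it.
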